**Technical merit. Project Overview.** We will build on our ongoing partnerships with people living in Alabama's Black Belt, learning together how to improve outcomes for individuals with diabetes. In the first year of the study we will conduct focus groups with people with diabetes and medication nonadherence to learn more about their beliefs and attitudes toward living with diabetes and the medications used to treat the disease. Using this information and working within the Corbin and Strauss framework, we will collaboratively create DVDs of peer storytelling integrated into a diabetes education experience, and the peer coaching protocol, drawing on Social Cognitive Theory and Adult Learning Theory. We will pilot test the intervention, and we will implement the randomized controlled trial (RCT) comparing the effectiveness of the intervention with usual care. In years 2 and 3, we will recruit 500 individuals with diabetes who report medication nonadherence, group randomize them to one of the 2 trial arms, and collect baseline and follow-up data 6 months later. Control patients will receive comprehensive diabetes education on conclusion of the 6 month period. During all 3 years, we will also work with community coalitions in our partnering communities to obtain ongoing input, share knowledge of community resources, create a resource bank website to facilitate the peer coaches' work, and plan for dissemination of the interventions.

Figure 3. Partnering communities in the Alabama Black Belt: North ([name]), Western ([name]), South Central ([name]).

**The setting and our partnership.** Booker T. Washington described the Black Belt as “a part of the country which was distinguished by the colour of the soil. The part of the country possessing this thick, dark, and naturally rich soil was, of course, the part of the South where the slaves were most profitable, and consequently they were taken there in the largest numbers. Later and especially since the (Civil) war, the term seems to be used wholly in a political sense—that is, to designate the counties where the black people outnumber the white.” The Black Belt runs in an arc across central Texas up to Maryland. In Alabama, it is a 200-mile wide belt across the southern half of the state (Figure 3).

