### Secondary Outcomes

Secondary outcomes will be health-related quality of life and self-efficacy. *Quality of life* will be assessed through the validated Short-Form 12 (SF-12), a generic measure of health-related quality of life. We will assess diabetes-specific quality of life using the validated Diabetes Distress Scale. *Self-efficacy* in taking medications will be assessed using the Self-efficacy for Appropriate Medication Use and the Perceived Diabetes Self-Management Scale, which is associated with A1c.

We will also assess the number of physician office visits, hospital stays and emergency visits in the previous 6 months, but do not anticipate that the short duration of the study will be able to detect significant differences between trial arms. Nevertheless, we will collect these data to build toward future longer term intervention studies. In addition, during the in-home visit we will transcribe the name and dose of all diabetes, blood pressure and lipid medications at baseline and follow-up to detect whether regimens have been intensified as a result of exposure to the interventions.

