## Participant Retention

During the 6 months of the trial, UAB staff will contact all participants 2-3 times. During these brief 5-minute calls, the staff will answer participant questions, update contact information, and provide help if needed in accessing study education materials. Participant retention plan will be a mixture of telephone and mail contacts as shown below:

Month	Control Participants	Month	Intervention Participants
1	Phone Call: Welcome to the study, answer questions	1	No contact
2	Postcard: Reminder to look at videos	2	Phone Call: answer questions, identify problems, update contact information
3	Phone Call: answer questions, identify problems, update contact information	3	No contact
4	Postcard: Keep in touch post card card	4	No contact
5	Phone Call: answer questions, identify problems, update contact information	5	Phone Call: answer questions, identify problems, update contact information
6	Postcard: reminder of upcoming data collection	6	No contact
All participants will receive postcards for birthdays, holiday cards (Thanksgiving, Christmas)			

During month 6 (control participants) or after the final session with the peer advisor (intervention participants), study staff will contact the participant to schedule their follow-up telephone interview and in-person data collection. Copies of postcards and telephone contact scripts are included in Appendix G.

The figure below shows the study flow from recruitment to the completion of the study.

LivingWell-FlowChart-v.2016-01-12

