## **Safety Assessments**

This study does not involve any new treatments of care, but rather focuses on standard care delivered in a new way. It is possible that the interventions will result in better compliance with medication treatment, resulting in over-control of diabetes or blood pressure. This could result in low blood sugar or low blood pressure and resultant symptoms. Therefore, we will monitor potential adverse events of this nature. We will monitor symptoms of low blood sugar in both trial arms at the follow-up data collection point as well as at ongoing contacts during the 12-week intervention phase, by peer coaches. During these contacts, symptoms of low blood sugar and low blood pressure will be assessed and reported to the investigators and to the participant's physician. If symptoms are present, the peer coach will refer participants to their primary care provider for evaluation immediately, assisting with the telephone call if needed.

Data on safety endpoints will be reviewed by a board convened for this purpose. Quarterly reports will be presented to the board over the course of the trial. The board will be constituted by 3 individuals experienced in the conduct of clinical trials and the safety of human subjects. Adverse events will be reported to the UAB IRB, and the NIH Office of Biotechnology Activities (OBA) in accordance with regulations, by the PI.

[name] and project investigators, including our community team members, will have an initial organizational meeting or conference call to discuss the protocol development, review of scientific, safety and ethical issues

related to the study design and approve plans for data integrity. After the initial planning meeting project investigators will be convened monthly in a meeting or conference call throughout the project period.

[name] will be responsible for monitoring the safety and efficacy of the study, executing the data and safety monitoring plan, and complying with the reporting requirements. She will provide a summary of the DSM report to PCORI on an annual basis as part of the progress report. The report will include participant's sociodemographic characteristics, expected versus actual recruitment rates, any quality assurance or regulatory issues that occurred during the past year, summary of adverse events, and any actions or changes with respect to the protocol. The DSM report to PCORI will also include, when available, the results of any efficacy data analysis conducted.

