
Project investigators will be primarily responsible for protecting the safety of the study participants and the scientific credibility of the project, and the validity of the assessment of the efficacy of the interventions used in the projects. The project investigators will also formulate recommendations relating to the selection, recruitment and retention of participants, their management, improving adherence to protocol-specified regimens, and the procedures for data management and quality control.

The entire project team will monitor success of recruitment, assess data integrity, and most importantly monitor for adverse events. Risks to study participants relate mostly to misinterpretation of what is research and what is usual care and loss of confidentiality. Project investigators will carefully evaluate how the study is described and assure that study subjects are informed not to report urgent symptoms (chest pain) through email communications. Any hospitalizations or deaths discovered by the research team will be promptly reported to the DSMB with an assessment of whether any study procedures may have contributed to these outcomes.

The risks of the study are low, and thus the safety monitoring plan has been matched to the risk to subjects in this study. Risks to physician study participants relate mostly to misinterpretation of what is research and what is usual care and loss of confidentiality. We are encouraging physicians and their staff to increase their provision of care related to diabetes, osteoarthritis and chronic pain to be consistent with current guidelines. However, we are not asking the physicians or their staff to provide services beyond those in standard, high-quality medical practices.

For this study, we plan interim data analysis twice annually to assess probability of statistically significant group differences. We will first compare baseline data to assure adequacy of randomization. We will then conduct interim analyses that will coincide with practice data intervals, and set intervals for patient data collection for outcomes data. Prior to interim analyses, investigators will assign stopping rules. Safety data to be included in these reports include hospitalization rates as well as Emergency Room utilization.

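### On-study hospital stays and emergency visits are systematically asked about only at month 6, and the reported rates have no defined denominator, so early safety rates may be understated and unequal between arms

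*Combined protocol and SAP*

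**What the plan says.** Safety Assessments plans interim work on a half-yearly cycle ("we plan interim data analysis twice annually to assess probability of statistically significant group differences") and ends that paragraph with the safety content: "Safety data to be included in these reports include hospitalization rates as well as Emergency Room utilization". It gives no denominator, reporting window or data source for these rates. The same section says of the board: "Quarterly reports will be presented to the board over the course of the trial", and sets up an event-by-event route: "Any hospitalizations or deaths discovered by the research team will be promptly reported to the DSMB".

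The scheduled source is under Secondary Outcomes: "We will also assess the number of physician office visits, hospital stays and emergency visits in the previous 6 months". The Project Overview in Background and Significance fixes the data collection points: "collect baseline and follow-up data 6 months later". A baseline answer covers time before enrolment, so scheduled on-study capture happens once, at month 6.

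Between those points, Participant Retention describes brief staff calls in which "the staff will answer participant questions, update contact information, and provide help if needed in accessing study education materials". Its table adds identifying problems as a purpose of most of these calls: control calls fall in months 1, 3 and 5, intervention calls in months 2 and 5. Intervention participants also have 13-16 peer contacts (Living Well with Diabetes Program Description). For safety, Safety Assessments has these contacts assess symptoms of low blood sugar and low blood pressure. The check-in scripts in the Peer Advisor Manual, as far as they were available, ask in general terms how the client is doing and about homework. They contain no question on hospital or emergency use.

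**The concern.** A rate needs a defined way of finding events and a matching denominator. Here the systematic source arrives six months after enrolment, while the reports run through the recruitment period. If the person preparing a report divides known events by everyone enrolled, or by all person-time accrued, most of the early denominator belongs to people who have not been asked. The rate then looks low early and climbs as interviews come in, with no change in risk.

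The second problem is comparability. What is discovered between visits depends on how often someone speaks to the participant, and that differs by arm. An early excess in the intervention arm could be real or could reflect more contact. The plan itself anticipates over-control of diabetes or blood pressure from better adherence, so this is a comparison the board would want to trust.

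**Working it through.** The documents state no hospitalization or emergency-visit rate, so there is no figure to reproduce. The check asks what fraction of a constant true rate a report would show.

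**Inputs from the documents.** 500 participants ("In years 2 and 3, we will recruit 500 individuals with diabetes who report medication nonadherence"); 6 months on study; 20% attrition (Power Calculations and Sample Size); call months as listed above.

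**Assumptions.** Uniform accrual; a constant event rate; the 20% without a follow-up interview count as full exposure; a share *q* of events not covered by a completed interview is discovered some other way. The documents give neither the accrual length nor *q*, so accrual of 12, 18 and 24 months and *q* = 0, 0.2 and 0.5 were tried.

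**Formula.** Let *r* be the monthly enrolment and *t* the months since first enrolment, with *t* of at least 6 and accrual still open.

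- Accrued person-months: *r* × [6(*t* − 6) + 6²/2] = *r*(6*t* − 18).
- Covered by completed interviews: 0.8 × *r* × 6(*t* − 6).
- Coverage *c* is the second divided by the first; *r* cancels. Month 6: 0/18 = 0. Month 9: 14.4/36 = 0.40. Month 12: 28.8/54 = 0.53. Month 18: 57.6/90 = 0.64. After the last interview: 0.80.
- Reported/true ratio: *c* + *q*(1 − *c*).
- With 6 months per enrolled participant as denominator and *q* = 0: 0.8(*t* − 6)/*t*.

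| Month | Person-time, q = 0 | Person-time, q = 0.2 | Person-time, q = 0.5 | Per enrolled participant, q = 0 | Interviewed only |
|---|---|---|---|---|---|
| 6 | 0 | 0.20 | 0.50 | 0 | no rate yet |
| 9 | 0.40 | 0.52 | 0.70 | 0.27 | 1.00 |
| 12 | 0.53 | 0.63 | 0.77 | 0.40 | 1.00 |
| 18 | 0.64 | 0.71 | 0.82 | 0.53 | 1.00 |
| End | 0.80 | 0.84 | 0.90 | 0.80 | 1.00 |

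Values through month 12 are the same for all three accrual lengths. The month 18 row needs accrual of at least 18 months. The last column counts only interview-reported events among interviewed participants.

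**Unequal discovery.** Suppose half of the uncovered events are discovered in the intervention arm and one fifth in control (illustrative values), with equal true rates and accrued person-time as denominator. The apparent rate ratio is 0.50/0.20 = 2.5 through month 6, 0.70/0.52 = 1.35 at month 9, 0.767/0.627 = 1.22 at month 12 and 0.90/0.84 = 1.07 at the end.

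**Effect of asking on the existing calls**, if every call and interview is completed. At month 6 the accrued time is 18 per unit of *r*. Time to the last ask is 1×2 + 3×2 + 5×1 = 13 in control (72%) and 2×3 + 5×1 = 11 in intervention (61%). At month 12 it is (36 + 13)/54 = 91% and (36 + 11)/54 = 87%, against 36/54 = 67% for the month-6 question alone on the same basis. Missed calls would lower these figures.

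**The case against.** The strongest reply is that the plan never sets the denominator that produces the trend. With interviewed participants only, the expected ratio is 1.00 at every report once interviews exist, and nothing in the plan excludes that choice. This stands: the bias is conditional, and the plan's gap is the missing definition.

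Second, discovered hospitalizations and deaths reach the DSMB promptly and individually, so the most serious events need not wait for month 6. Retention calls meant to identify problems, frequent peer contacts and weekly staff contact with the peers could all surface a hospital stay. This also stands, and it means the *q* = 0 column is a lower bound for hospitalizations. It does not supply a rate, because the captured share is unknown and probably higher in the intervention arm. No equivalent route is named for emergency visits.

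Third, the telephone interview (Appendix E) and the retention scripts (Appendix G) were not in the part of the document available for this review. A question may already be there, so the fix is conditional on checking.

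Fourth, the quarterly board reports are not said to carry these rates, and the interim analyses are to coincide with practice data intervals and set patient data collection intervals. The month 9 figure therefore matters only if a report falls then. No collection of practice data is described in the available text, so that phrase does not identify another source.

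Finally, the plan describes its risks as low and monitors low blood sugar and low blood pressure symptoms separately. That argues for a light remedy.

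**Conclusion.** The point holds in a limited form. In the available text, on-study hospital and emergency use is systematically collected once, at month 6, while the interim reports must show it as rates. Interim discovery is unscheduled and likely to differ by arm, and no denominator is stated. Over accrued person-time with no interim discovery, the reported/true ratio is 0 through month 6, about 0.40 at month 9, 0.53 at month 12 and 0.80 at the end. This rests on uniform accrual, a constant true rate and the plan's 20% attrition counted as full exposure.

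A reader might infer that reported rates must start near zero and rise by construction, and that the board would be blind to early admissions. The documents do not support that: it needs a denominator they do not set and no discovery between visits, whereas discovered hospitalizations and deaths are to be reported promptly. This is a worthwhile, inexpensive improvement to the monitoring plan; it does not show that the safety reports will be wrong.

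**What to change.** First check the Appendix G scripts. Unless they already do this:

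1. Ask the same scripted question on hospital stays and emergency visits at every existing retention call in both arms (months 1, 3 and 5 in control; 2 and 5 in intervention) and at month 6. Record event dates so that an event reported twice is counted once.
2. In each report, give rates by arm per person-month, with each participant's time running to the last completed ask.
3. List deaths, and events found in any other way, separately by arm and outside the rate, so that they still reach the board.
4. State in Safety Assessments which reports carry these rates.

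If no question is added, the rate can be restricted to participants with a completed 6-month interview, using their 6 months as denominator. Use this only with the separate listing in step 3, because it drops those who died or were lost, and it gives no rate until interviews exist.

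The cost is about one minute on calls that staff already make, plus a little extra reporting work. No added staff or visits are needed.

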## Appendix A

### **General Health Education Video Handout**

# General Health Education Program Videos

- **Video 1: Alzheimer's and Dementia**
- **Video 2: Breast Cancer**
- **Video 3: Colorectal Cancer**
- **Video 4: Osteoporosis and Fall Prevention**
- **Video 5: Eye Care**
- **Video 6: Oral Health**
- **Video 7: Foot Care**
- **Video 8: Driving Safety**

We are so glad to have you in our program!

Here is a list of the videos that are included on this DVD.

For questions, please call the UAB Study Team at [contact]

## Appendix B

### **Peer Advisor Candidate Screening Form**

## Peer Advisor Interest Talking Points / Screening Form

Date of Discussion: \_\_\_\_\_

Name of Potential Peer: \_\_\_\_\_

Peer's Community: \_\_\_\_\_

Phone Number: \_\_\_\_\_

Phone Number: \_\_\_\_\_

---

### What is Living Well with Diabetes?

Diabetes is a big problem in rural Alabama, especially in the Black Belt. The Black Belt has among the highest rates for diabetes and diabetes complications such as heart attack, stroke, kidney disease, amputation, and eye problems. Many people who have diabetes do not take their medications every day. Taking your diabetes medications every day as directed by your doctor is one of the ways that can help you live as well as you can, as long as you can.

The goal of the study is to help people take care of their diabetes by taking their medications every day as directed by their doctor, eating healthy foods, exercising, having effective interactions with their healthcare team, reducing stress, and getting positive support from family and friends. We think that this program will help people with diabetes live as well as they can, as long as they can.

### What is a Peer Advisor?

Peer Advisors are people who live in the Black Belt and want to help their communities. We are looking for people with diabetes, or people who care for someone who has diabetes. The essentials: you care about your community, you want to help, and you have familiarity with what it is like to live with diabetes day in and day out.

### How long would I be involved?

The Living Well with Diabetes study will last approximately 1 to 1.5 years.

### Do I have to participate until the program ends?

We are looking for people who would be willing to work with us for at least one year.

### What would I need to do?

#### *Getting Trained and Certified as a Peer Advisor*

- Attend 2 days of in-person training, followed by a 10-week telephone training.
  - Costs you nothing
  - Learn about diabetes basics, motivational interviewing, talking to the doctor, medications for diabetes, blood pressure, and cholesterol
  - Practice your new skills. **NOTE: It is easier for some people to develop these skills than it is for others. There will be a test at the end of the 2 days of in-person training to see how much you have mastered. Unfortunately, some people may not move on to become Peer Advisors.**

- Time Commitment for Training:
  - 2 In-person trainings: 6 hours each day, lunch will be provided
  - 10-Week Telephone Training: 2 to 4 hours each week, depending on the week
    - 30-60 minutes listening to audio recording of the session and watching session video
    - 30-60 minute telephone call with the other peer advisor candidates
    - 30 minutes roleplaying as a client
    - 30 minutes roleplaying as peer
    - 30-60 minutes talking with UAB staff, providing feedback on the program, and completing certifications
    - *(as needed)* additional practice time with the community coordinator in order to complete certification

### ***Working as a Peer Advisor***

- Work with someone with diabetes on the phone for 5 months, one-on-one, over the phone.
- Time Commitment as a Peer Advisor:
  - First 2 months: talk with client on the telephone weekly (30-45 minutes per call)
  - Last 3 months: bi-weekly or monthly (10-20 minutes per call)
  - Special call before and after a doctor visit (10-15 minutes each call)
- Attend a weekly group call with other peer advisors (30-45 minutes)
- Speak with a UAB staff member every 1-2 weeks (15-30 minutes)

### **What's in it for me?**

Peer advisors will be UAB employees.

- \$50 Gift card for completing the 1st in person training, whether or not you pass the test (1 day)
- \$50 Gift card for completing the 2nd in person training, whether or not you pass the test (1 day)
- \$250 Gift card for completing the 10 week telephone training, whether or not you pass the test
- \$150 for completing the program with each study participant.

